11.6 Early Withdrawal from the Study

Patients, their relatives, their representatives or the patients' physician may withdraw the patient from the study at any time if they feel the study is not in the patients' best interest, or they may be withdrawn by the investigator or sponsor for safety, behavioral, or administrative reasons. All withdrawals must be fully documented.

If the patient withdraws from the study and also withdraws consent for the disclosure of future information, no further evaluations should be performed and no additional data should be collected. Previously acquired data will be analyzed. This will not have any effect on the treatment that the patient receives.

11.7 Expected Duration of Recruitment

The study is planned for a duration of approximately 12-18 months

Exalenz Bioscience Ltd.	Last update on: Nov 21, 2016
Study Title: Clinical Study of the BreathID[®] MCS System to train the algorithm for the ¹³C-Methacetin Breath Test (MBT) in assessment of Portal Hypertension in Patients with Compensated Liver Cirrhosis	Protocol No.: CSPH-EX-0414 Version: 1.5
Document N°: CSD00076	Page 38 of 72

12 STATISTICAL CONSIDERATIONS

12.1 Study Design and Objectives

This is a multicenter, non-randomized, blinded, cross-sectional comparative exploratory study comparing various MBT measures to HVPG.

This study will be used to train an algorithm using MBT measures and to select a cut-off to determine presence or absence of CSPH as defined by HVPG \geq 10mmHg.

The modeled algorithm will be validated in a separate study

12.2 Primary endpoints

Binary diagnosis of CSPH, defined as HVPG \geq 10 mmHg, correlated with an MBT result to be developed.

The relationship will be assessed on both sides of the definitive HVPG value to obtain a clinically significant MBT model/algorithm and its cut-off to be validated in a separate study.

12.3 Secondary efficacy endpoint

1. Binary diagnosis of portal hypertension with HVPG \geq 12mmHg
2. Binary diagnosis of portal hypertension with HVPG \geq 20mmHg
3. Correlation of MBT with HVPG readings
4. Assess the effect of beta blockers or other confounding factors on the correlation of MBT with HVPG readings
5. Examine the effect of a single small (<3cm) HCC (hepatocellular carcinoma) on the correlation of MBT with HVPG tracings

12.4 Safety Endpoints

All Adverse Events.

12.5 Sample Size estimation

As presented in section 5.6 above the MBT parameter CPDR15 was found to have an AUC of about 0.9. Two hundred (200) subjects of which at least 50 will be positive for CSPH and at least 50 will be negative for CSPH will enable the estimation of a more conservative AUC of 0.85 with a half width of the 95% confidence interval of 0.1, if the ratio of positive to negative subjects is as high as 3:1 and as low as 1:8 (1 pos. per 7 neg.).

Exalenz Bioscience Ltd.	Last update on: Nov 21, 2016
Study Title: Clinical Study of the BreathID[®] MCS System to train the algorithm for the ¹³C-Methacetin Breath Test (MBT) in assessment of Portal Hypertension in Patients with Compensated Liver Cirrhosis	Protocol No.: CSPH-EX-0414 Version: 1.5
Document N°: CSD00076	Page 39 of 72

During the study the correlation between MBT and HVPG will be assessed periodically in order to see if the intake of beta blockers, HCC or any other confounding factors have an effect on the breath test result. If the population using beta blockers, HCC or if some other confounding factor shows a significantly different correlation than the rest of the population, the study population may be increased up to 400 patients.

12.6 Analysis sets

All subjects enrolled to the study.

12.7 Statistical Analysis

12.7.1 General Considerations

Statistical analyses will be performed using SAS[®] v9.3 or higher (SAS Institute, Cary NC, USA).

If any statistical tests are performed, they will be two-sided. The required significance level of findings will be equal to or lower than 5%. Where confidence limits are appropriate, the confidence level will be 95%.

Baseline values are defined as the last valid value prior to study treatment start.

All statistical analyses of safety and performance measures will be descriptive in nature. Continuous variables will be summarized by a mean, standard deviation, minimum, median and maximum, and categorical variables by a count and percentage. Confidence intervals will be provided where relevant.

If multiple measurements are taken in a single patient, statistics described below will be appropriately modified to accommodate the within patient correlation.

12.7.2 Demographic and Other Baseline Characteristics

Demographic, medical and clinical history variables will be tabulated. Continuous variables will be summarized by a mean, standard deviation, minimum, median and maximum, and categorical variables by a count and percentage.

12.7.3 Disposition of Subjects

The numbers of patients who were enrolled will be provided, as well as the reasons for all enrollment discontinuations, grouped by major reason (e.g., lost to follow-up, adverse event, poor compliance). A list of discontinued patients, protocol deviations, and patients excluded from the efficacy analysis will be provided as well

Exalenz Bioscience Ltd.	Last update on: Nov 21, 2016
Study Title: Clinical Study of the BreathID[®] MCS System to train the algorithm for the ¹³C-Methacetin Breath Test (MBT) in assessment of Portal Hypertension in Patients with Compensated Liver Cirrhosis	Protocol No.: CSPH-EX-0414 Version: 1.5
Document N^o: CSD00076	Page 40 of 72

12.7.4 Safety Analysis

The events related to study drug and/or device AE's rate will be presented along with a 95% exact binomial two sided 95% confidence interval. The analysis of all adverse events will include incidence tables and will include analyses by severity, relationship to device or drug and baseline variables.

12.7.5 Performance Analysis

A model/algorithm will be developed for the differentiation between subjects with and without CSPH, defined as HVPG ≥ 10 mmHg. It will be developed using either logistic regression or neural network or any other known methodology. Using a cut-point on the score a binary diagnosis of CSPH (Y/N) will be obtained. The minimal criterion for sufficient efficacy is an Area under the Receiver Operating Curve (AUC) ≥ 0.85 in this patient population. A potential clinical utility was designated for the algorithm/model output; where this algorithm could aid the clinician in ruling-out CSPH. This will be translated into finding a model prediction cut-point that provides a high sensitivity (true positive rate) and at least moderate specificity (true negative rate), which in turn achieves a high negative predictive value (NPV). High NPV is considered to be near 90% (i.e. 88%) thus sensitivity should be at least 90% and specificity should be at least 50%. Cross validation methods will be used to test algorithm stability.

12.7.6 Interim Analysis

This study is an open label study for training purposes. The data may be assessed prior to achieving the full sample size. This will be done specifically in order to assess the effect of beta blockers, HCC, or any other confounding factor on the correlation between MBT and HVPG. If beta blocker, HCC or if some other confounding factor shows significantly different correlation than the rest of the population, the study population may be increased up to 400 patients.

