Secondary:	
 1. Binary diagnosis of portal hypertension with HVPG ≥ 12 mmHg 2. Binary diagnosis of portal hypertension with HVPG ≥ 20 mmHg 3. Correlation of MBT with HVPG readings 4. Assess the effect of beta blockers or other confounding factors on the Correlation of MBT with HVPG readings 5. Examine the effect of a single small (<3cm) HCC (hepatocellular carcinoma) on the correlation of MBT with HVPG tracings
Safety Endpoints:	Safety will be assessed by all adverse and serious adverse events occurring in all subjects enrolled throughout the duration of the study.
Study Design:	A multicenter, non-randomized, blinded, cross-sectional comparative exploratory study comparing various MBT measures to HVPG. This study will be used to train an algorithm using MBT measures and to select a cut-off to determine presence or absence of CSPH as defined by HVPG ≥ 10 mmHg.

Exalenz Bioscience Ltd.	Last update on: Nov 21, 2016
Study Title: Clinical Study of the BreathID[®] MCS System to train the algorithm for the ¹³C-Methacetin Breath Test (MBT) in assessment of Portal Hypertension in Patients with Compensated Liver Cirrhosis	Protocol No.: CSPH-EX-0414 Version: 1.5
Document N^o: CSD00076	Page 12 of 72

Study Population^a:

At least 200 consecutive compensated cirrhotic patients, defined as cirrhotic patients without complications^b and meeting all inclusion/exclusion criteria will be enrolled on a walk-in basis. If beta blockers or HCC or other confounding factors affect the correlation between MBT and HVPG the sample size may be enlarged following interim analysis.

Inclusion Criteria:

1. Adult men or women (≥ 18 years of age)
2. Patient (or legal guardian) can sign an Informed Consent Form
3. Known chronic liver disease with cirrhosis confirmed by either:
 - a. liver biopsy or
 - b. clinical (palpable left lobe, splenomegaly) and laboratory (platelets $< 150,000/\text{mm}^3$ or albumin $< 3.8\text{g/dL}$, or INR > 1.3) evidence of cirrhosis and/or
 - c. imaging studies by abdominal sonography, computer assisted axial tomography, or magnetic resonance imaging, showing a nodular liver and/or enlarged spleen and/or portosystemic collaterals with portal vein patency and/or minimal ascites, and/or colloid shift on a colloid-isotope liver-spleen scan or measurements of liver stiffness suggestive of cirrhosis
4. Europe: Indicated to undergo HVPG testing
US: Consented for HVPG
5. Can tolerate an overnight (8-hour) fast

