10.3 Secondary Objectives

1. To assess the ability of the MBT model to diagnose portal hypertension with HVPG \geq 12mmHg
2. To assess the ability of the MBT model to diagnose portal hypertension with HVPG \geq 20mmHg
3. To assess the correlation of MBT with HVPG readings

Exalenz Bioscience Ltd.	Last update on: Nov 21, 2016
Study Title: Clinical Study of the BreathID[®] MCS System to train the algorithm for the ¹³C-Methacetin Breath Test (MBT) in assessment of Portal Hypertension in Patients with Compensated Liver Cirrhosis	Protocol No.: CSPH-EX-0414 Version: 1.5
Document N°: CSD00076	Page 34 of 72

4. To Assess the effect of beta blockers or other confounding factors on the correlation of MBT with HVPG readings
5. Examine the effect of a single small (<3cm) HCC (hepatocellular carcinoma) on the correlation of MBT with HVPG tracings

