10.4 Efficacy Endpoints

10.4.1 Primary efficacy endpoint

Binary diagnosis of CSPH, defined by HVPG ≥ 10 mmHg, correlated with an MBT result to be developed.

The relationship will be assessed on both sides of the definitive HVPG value to obtain a clinically significant MBT model/algorithm and its cut-off to be validated in a separate study.

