10.4.2 Secondary efficacy endpoint

1. Binary diagnosis of portal hypertension with HVPG ≥ 12 mmHg
2. Binary diagnosis of portal hypertension with HVPG ≥ 20 mmHg
3. Correlation of MBT with HVPG readings
4. Assess the effect of beta blockers or other confounding factors on the correlation of MBT with HVPG readings
5. Examine the effect of a single small (<3cm) HCC (hepatocellular carcinoma) on the correlation of MBT with HVPG tracings

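### The confounder check compares only MBT-HVPG correlations, which do not respond to a constant shift, and cut-off performance is not split by beta-blocker or HCC status

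*Combined protocol and SAP*

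**What the plan says.** Section 12.5 describes a periodic look whose purpose is to see whether beta-blocker intake, "HCC or any other confounding factors have an effect on the breath test result". The decision sentence that follows is narrower. It applies when a subgroup "shows a significantly different correlation than the rest of the population", and it then permits enlargement. Section 12.7.6 repeats it: the condition is a factor that "shows significantly different correlation than the rest of the population, the study population may be increased up to 400 patients". The synopsis, under Study Population, uses the same measure: if "confounding factors affect the correlation between MBT and HVPG the sample size may be enlarged following interim analysis".

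The matching secondary objectives and endpoints are also about correlation. Item 4 is "To Assess the effect of beta blockers or other confounding factors on the correlation of MBT with HVPG readings" and item 5 is "Examine the effect of a single small (<3cm) HCC (hepatocellular carcinoma) on the correlation of MBT with HVPG tracings". No test is named. Section 5.6 reports the MBT-HVPG correlation as r: -0.75 for PDR45 in 21 patients and -0.57 for CPDR15 in 58.

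The product of the study is a single cut-off. Section 12.7.5 asks for a high NPV, "thus sensitivity should be at least 90% and specificity should be at least 50" percent, and Section 10.4.1 describes "a clinically significant MBT model/algorithm and its cut-off to be validated in a separate study". The synopsis (Data Analysis / Statistics) requires sensitivity, specificity, PPV and NPV with exact intervals for all efficacy analysis, without naming a split by beta-blocker or HCC status. The only planned subgroup regression of the primary endpoint, in 12.7.7, is by center.

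**The concern.** The stated aim and the decision measure do not match. A factor can affect the breath test result by moving its level at a given HVPG while leaving the strength of the association unchanged. A comparison of correlations does not address that effect, yet it is the one that changes accuracy at a common cut-off.

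The documents make one such effect plausible. Section 5.2 and its Table 1 describe HVPG as tracking response to portal-pressure-lowering drugs, with beta blockers listed. Section 5.5.1 says MBT also depends on hepatocyte damage. If a beta blocker lowers HVPG and MBT does not fully follow, users sit at a different MBT level for the same HVPG. Patients on stable beta blockers and patients with a single small HCC are eligible, and the plan itself names both as possible confounders. At stake is whether the cut-off goes into the validation study without having been examined in those two groups.

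**Working it through.** **Plan's own figures.** The plan attaches no number to the confounder rule. The nearest figures are the targets of 12.7.5. NPV = Sp(1-p) / [Sp(1-p) + (1-Se)p]. With Se 0.90, Sp 0.50 and p = 0.40 this is 0.30 / (0.30 + 0.04) = 88%, so the stated 88% corresponds to a CSPH prevalence of 40%.

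**Step 1: what a correlation sees.** corr(H, M + d) = cov(H, M) / [SD(H) SD(M)] = corr(H, M) for any constant d. The same holds if the constant is added to HVPG, and a rank correlation within the subgroup is also unchanged. This is exact at any sample size.

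**Step 2: inputs.** r = -0.75 is from Section 5.6. HVPG mean 12 and SD 5 mmHg, a 3 mmHg lowering, and 10 to 30% of patients in the subgroup are assumptions; the documents give none of them. Model: M = r(H - 12)/5 + sqrt(1 - r²)e, with M in SD units. It gives an AUC of 0.86, so it meets the 0.85 criterion of 12.7.5.

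**Step 3: accuracy at the cut-off.** Se = average of Φ[(c - E(M|H)) / sqrt(1 - r²)] over H ≥ 10; Sp = 1 minus the same average over H < 10. The cut-off c is set for Se = 90% in patients without the factor. Prevalence is Φ(0.4) = 66% in those patients and Φ(-0.2) = 42% in a subgroup with mean HVPG 9. Lowering HVPG by 3 with MBT unchanged equals an MBT shift of 0.75 × 3/5 = 0.45 SD at a given HVPG.

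| Group | Se | Sp | NPV |
|---|---|---|---|
| Without the factor | 90% | 58% | 75% |
| Subgroup, HVPG lowered 3 mmHg, MBT unchanged | 96% | 43% | 94% |
| Same, cut-off refitted on pooled data, 25% subgroup | 95% | 45% | 93% |

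An unspecified MBT shift of 0.34 or 0.5 SD would give Sp of 41% or 33% in the same direction, and Se of 80% or 74% in the opposite one. The second direction is shown only for scale.

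**Step 4: detection.** The correlation comparison is z = (atanh r1 - atanh r2) / sqrt[1/(n1-3) + 1/(n2-3)]. The alternative regresses M on (H - 10), factor, and factor × (H - 10), with a joint 2-df F test of the last two terms. Two-sided 5% level, 10,000 replicates per cell, HVPG lowered 3 mmHg, subgroup 10/20/30%:

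| Case | Correlation comparison | 2-df regression |
|---|---|---|
| r = -0.75, N = 100 | about 5% throughout | 40/64/75% |
| r = -0.75, N = 200 | about 5% throughout | 71/92/97% |
| r = -0.57, N = 200 | about 5% throughout | 32/53/63% |

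With no factor effect both tests reject at about 5%. The case r = -0.57 is used for power only, because its AUC of 0.77 misses 12.7.5 before any shift.

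**Step 5: where the 5% does not hold.** It needs equal HVPG spread in the two groups and a linear relation. With a subgroup SD of 4 or 3 instead of 5 (N = 200, 25% subgroup, 0.34 SD shift), the correlation comparison rejects about 16% or 53% of the time. By Step 1 this is due to the spread, not the shift. With a curved relation (0.15 z² term), a subgroup mean 3 mmHg higher and no factor effect, it rejects 18/23% (20/30% subgroup). The linear 2-df test is misled too, at 26/31%; adding an HVPG-squared term brings it back to 5/6%.

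**The case against.** *Correlation may be meant loosely.* The primary endpoint calls a binary diagnosis correlated with an MBT result, the next sentence speaks of a relationship, and the aim in 12.5 would fit a comparison of levels. This stands in part. No test is defined, so the defect is certain only on the reading as r. Section 5.6 uses that reading, and nothing in the statistical section points to another.

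*Accuracy measures are already required.* The synopsis asks for them in all efficacy analysis, and items 4 and 5 are listed as efficacy endpoints. It would therefore be wrong to infer that the plan never asks for cut-off performance. What is missing is any statement that it is shown by beta-blocker or HCC status.

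*The harm is speculative.* A reader might infer that beta-blocker or HCC patients with CSPH would be missed. The documents do not support that. The mechanism they make plausible raises sensitivity and, under the assumed values, NPV, which is what rule-out use depends on; only specificity falls below its target. Section 5.5.1 also lists altered blood flow and shunting, so MBT may partly follow a pressure change and the shift would be smaller. For HCC the documents give no basis for a shift. Section 5.6 saw no beta-blocker effect, but on correlation in 21 patients, which cannot exclude one.

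*Little depends on the rule.* Enlargement is optional and would not remove a shift, the model form is open, the analyses are descriptive, and validation is separate. This stands and limits the severity.

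**Conclusion.** The point holds in a limited form. Read as a comparison of r, the rule does not respond to a constant shift of MBT at a given HVPG. With equal spread and linearity it rejects at about 5% whatever the shift; otherwise it can fire for reasons unrelated to one. It would overstate the case to say that it never rejects above 5%, or that a shift is present.

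Under the assumed values, the mechanism the documents make plausible gives Se 96% and Sp 43% in the subgroup against a 50% specificity target. The NPV of 94% is partly due to the lower prevalence there, and the base case (75%) already misses the 88% figure without any shift. Subgroup size and shift size are assumptions throughout. The change is worth making because it aligns the rule with its stated aim using data already collected, but the consequence for this training study is modest.

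**What to change.** - **12.5, 12.7.6 and the synopsis sentence.** Replace the correlation comparison with: for each factor, a prespecified MBT measure that is available at the interim (for example CPDR15, and the final score once developed) is regressed on HVPG centred at 10 mmHg, factor, and factor × HVPG. The factor is judged by the joint 2-df test at the two-sided 5% level. The estimated shift at 10 mmHg with its 95% CI is reported descriptively. An HVPG-squared term is added as a sensitivity analysis. Non-significance is not reported as absence of effect. The optional enlargement clause can stay.
- **12.7.5.** Add: once the cut-off is set, sensitivity, specificity, PPV and NPV at the common cut-off, with exact 95% CIs, are also reported by beta-blocker and HCC status.
- **Objectives and endpoints 4 and 5.** Change correlation to relationship.

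The cost is wording and slightly more analysis, with no added visits or procedures. Precision will be poor in small subgroups. At N = 200, a 25% subgroup with 33 CSPH and 17 non-CSPH patients gives exact intervals of about 76-98% for Se near 90% and 33-82% for Sp near 58%. A 10% subgroup (13 and 7) gives 64-100% and 18-90%. As with the present rule, the 5% level applies per factor and per look.

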12.7.7 Pooling

Subgroup analysis of the primary performance endpoint by center via a regression model will be used to evaluate the poolability of the results. If the variable by center analysis is found significant, the reason for this will be further explored and rationalized. This evaluation may include demographic features, symptoms at presentation, clinical and treatment history, and center comparability in the features found to be associated with the primary efficacy variable

12.7.8 Handling of Missing Data

The study variables cannot be evaluated for patients for whom MBT device results or HVPG results are not available and therefore these subjects will be left out of the efficacy analysis.

Exalenz Bioscience Ltd.	Last update on: Nov 21, 2016
Study Title: Clinical Study of the BreathID[®] MCS System to train the algorithm for the ¹³C-Methacetin Breath Test (MBT) in assessment of Portal Hypertension in Patients with Compensated Liver Cirrhosis	Protocol No.: CSPH-EX-0414 Version: 1.5
Document N^o: CSD00076	Page 41 of 72

Demographic clinical characteristics and safety data of patients with missing data will be compared to patients with complete data.

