Document N^o: CSD00076	Page 72 of 72

actual measurement. CO₂ production with ¹³C may be visible within a few minutes in cases with relatively functional livers.

Note: In rare cases the administration of fluids may cause vomiting. If this happens the test should be aborted and repeated the next day. The expected adverse event should be reported in the appropriate CRF section.

4. The patient should remain in a seated position breathing in a normal manner for up to 75 minutes, whilst data are collected.
5. The *BreathID[®] MCS* device continuously measures and analyzes the patient's exhaled breath in real time. As the ¹³C-Methacetin is metabolized, the value of the ¹³CO₂/¹²CO₂ ratio in the exhaled breath will change and will be calculated in real time by the *BreathID[®] MCS* device. The device will prompt the operator to enter patient details such as weight and height, age and gender. The *BreathID[®] MCS* device will calculate the *MBT* variables.
6. If at any time the device does not detect patient's breath, or if there is any other deviation from the desired test requirements, the device will produce an appropriate warning signal.
7. At the completion of the procedure, the cannula is removed and the patient is disconnected from the *BreathID[®] MCS* device.

The patient will be under the supervision of the physician or any other qualified medical staff during the entire test.

The operators will be trained how to terminate the breath test early. In the following situations, the *MBT* test will be terminated and a test termination form will be completed:

1. The patient vomits.
2. The patient is inadvertently disconnected.
3. The *BreathID[®] MCS* device malfunctions (In this case, the operator will complete a technical complaint form in addition to the test termination form and contact Exalenz immediately for further instructions)

In all these cases, the next *MBT* cannot be repeated the same day. An entry will be made in the drug/kit accountability log and the bottles will be kept for inspection by the study monitor.

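### Accuracy is reported only for patients in whom the breath test worked; unrepeated test failures should be counted and their effect bounded

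*Combined protocol and SAP*

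**What the plan says.** - **Analysis set.** Section 12.6 gives one set: "All subjects enrolled to the study". No evaluable set is defined.
- **Missing results.** Section 12.7.8 says of patients without an MBT or HVPG result that "these subjects will be left out of the efficacy analysis". It adds one check: "Demographic clinical characteristics and safety data of patients with missing data will be compared to patients with complete data".
- **Listing.** Section 12.7.3 promises a list in which "patients excluded from the efficacy analysis will be provided as well".
- **How a test can fail.** Appendix III ends the MBT early if the patient vomits, if the device malfunctions, or if "The patient is inadvertently disconnected". A termination form is completed each time.
- **Repeats.** After vomiting, "If this happens the test should be aborted and repeated the next day". After any early termination the next MBT "cannot be repeated the same day". Section 13.1 (item 7) allows the MBT up to 7 days before or after HVPG, and exclusion 20 in 11.2 removes patients who cannot perform it in that window. For patients with HCC, the note to 11.1 and 13.1 (item 7) require the MBT on the day of HVPG.
- **Criteria.** Section 12.7.5 states that "sensitivity should be at least 90% and specificity should be at least 50" percent, with an NPV of about 88%. Its minimal efficacy criterion is an AUC of at least 0.85.

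**The concern.** Vomiting, disconnection and malfunction are failures of the test under study. A patient with a valid HVPG and a failed, unrepeated MBT is someone in whom the test was tried and gave no answer. Under 12.7.8 that patient leaves both numerator and denominator. Nothing in the plan sets a failure rate as an outcome, says how a failed test is to be classified, or recalculates accuracy with failures counted. The comparison in 12.7.8 and the list in 12.7.3 make the losses visible, but they leave sensitivity, specificity and NPV as they are.

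Two features could hide or concentrate the losses. Exclusion 20 could turn a patient with a failed, unrepeated test into an ineligible one who is never counted as a failure. An HCC patient whose test is terminated must have the MBT on the HVPG day and may not repeat it that day, so unless HVPG is moved no compliant result is possible. The effect of HCC is a secondary endpoint (12.3) and a possible reason to enlarge the study (12.5), so these losses would fall on a group of interest.

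At stake is whether the 90% and 50% criteria are described as met.

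**Working it through.** **1. The plan's own figure, and whether lost precision is the problem.** Section 12.5 states a 95% half-width of 0.1 for an AUC of 0.85 with 200 subjects. By Hanley-McNeil, with A = 0.85, Q1 = A/(2−A) and Q2 = 2A²/(1+A),

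SE² = [A(1−A) + (n₁−1)(Q1−A²) + (n₀−1)(Q2−A²)] / (n₁n₀).

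The half-width 1.96 × SE is 0.053 at 150 positive/50 negative and 0.097 at 25/175, so the stated 0.1 is reproduced. Losing 5% of patients at 25/175 gives 0.0996; losing 10% gives 0.102. Precision is hardly affected. The question is what the estimates describe.

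**2. Inputs for accuracy.** Evaluable sensitivity Se = 0.90 and specificity Sp = 0.50, the 12.7.5 criteria. The failure rate f (no valid MBT after any repeat) is **assumed**, at 1% to 10% and equal in both CSPH classes, because the documents give none.

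**3. Three ways to score a failure.**
- (a) Wrong in both classes: Se(1−f) and Sp(1−f).
- (b) CSPH not ruled out, i.e. test positive: Se(1−f)+f and Sp(1−f).
- (c) Test negative: Se(1−f) and Sp(1−f)+f.

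| Assumed f | (a) wrong, Se/Sp % | (b) not ruled out, Se/Sp % | (c) negative, Se/Sp % |
|---|---|---|---|
| 1% | 89.1 / 49.5 | 90.1 / 49.5 | 89.1 / 50.5 |
| 2% | 88.2 / 49.0 | 90.2 / 49.0 | 88.2 / 51.0 |
| 5% | 85.5 / 47.5 | 90.5 / 47.5 | 85.5 / 52.5 |
| 10% | 81.0 / 45.0 | 91.0 / 45.0 | 81.0 / 55.0 |

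Each rule puts at least one measure below its criterion, but only (a) lowers both.

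**4. NPV.** Take a CSPH prevalence of 40% (assumed; it gives an evaluable NPV close to the plan's 88%) and f = 5%.
- Evaluable: 0.50×0.60 / (0.50×0.60 + 0.10×0.40) = 0.300/0.340 = 88.2%.
- (a): 0.475×0.60 / (0.475×0.60 + 0.145×0.40) = 0.285/0.343 = 83.1%.
- (b): numerator and denominator both shrink by (1−f), so 88.2%, unchanged.
- (c): 0.525×0.60 / (0.525×0.60 + 0.145×0.40) = 0.315/0.373 = 84.5%.

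**5. Margin needed.** Under (a), sensitivity stays at 90% only if the evaluable value is at least 0.90/(1−f): 91.8% at f = 2%, 94.7% at 5%. Under (a) or (b), specificity stays at 50% only if the evaluable value is at least 0.50/(1−f): 51.0% and 52.6%.

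**6. In patients.** With the 12.5 minimum of 50 per class and two failures in each, 44/48 = 91.7% sensitivity becomes 44/50 = 88.0% under (a) but 46/50 = 92.0% under (b). Specificity of 24/48 = 50.0% becomes 24/50 = 48.0% under either.

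**7. Is the complete-case figure biased for tested patients?** Not if failure is unrelated to the would-be result: sensitivity stays 90.0%. If would-be false negatives fail more often (10% against 3%), it reads (0.90×0.97)/(0.90×0.97 + 0.10×0.90) = 0.873/0.963 = 90.7%. If would-be true positives fail more often (6% against 3%), it reads 0.846/(0.846 + 0.097) = 89.7%. The sign is not known in advance.

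**The case against.** The strongest reply is that this is an exploratory training study. A patient without MBT data cannot train an MBT model, 12.7.1 calls the performance analyses descriptive, and performance in patients offered the test belongs chiefly to the separate validation study. That settles the choice of complete cases for fitting and for choosing the cut-off. It does not cover the reporting of accuracy against numerical criteria, which 12.7.5 and the synopsis both plan.

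Second, exclusion follows only if no valid repeat is obtained. Repeats are provided for, the window is 7 days either side of HVPG, Appendix III calls vomiting rare, and the device prompts for a badly fitted cannula. The loss may well be small. But no frequency is given for disconnection or malfunction, and an unknown rate is a reason to report it.

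Third, the table starts exactly at the criteria, so any failure rate above zero crosses at least one of them. That is true, and the table says nothing about how far this trial's results will lie from the criteria. The margins in step 5 are the more useful reading. Because the cut-point is chosen in these data to satisfy the criteria, results close to one of them would not be surprising.

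Fourth, scoring every failure as wrong matches no usable decision rule: it calls failed CSPH patients negative and failed non-CSPH patients positive, which requires the HVPG. This stands; (a) is a bound only.

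A reader might infer that sensitivity and specificity are both overstated. The documents do not support that. In the rule-out use of 12.7.5, a failed test most naturally leaves CSPH not ruled out, which raises sensitivity and lowers specificity. A reader might also infer that the 90%/50% targets pass to the validation study. Sections 10.4.1 and 12.1 send only the model or algorithm and its cut-off.

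**Conclusion.** The gap is real and modest. As written, the accuracy figures cover patients with a valid MBT and a valid HVPG, while the only named analysis set is everyone enrolled. They can overstate performance in patients offered the test, and the plan contains nothing to show by how much. At an assumed 5% failure rate, equal in both classes, with evaluable results at 90%/50%, sensitivity could lie between 85.5% and 90.5% and specificity between 47.5% and 52.5%, depending on the scoring rule. On the rule-out reading only specificity falls, by 2.5 points, and NPV does not change. Training of the algorithm and the precision of the AUC are not in question, and the AUC criterion was not re-examined with failures included.

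**What to change.** 1. Keep complete cases for training and cut-off selection, and define them beside 12.6 as an evaluable set (valid HVPG and valid MBT).
2. Add to 12.7.8 a sensitivity analysis of sensitivity, specificity and NPV in all patients with a valid HVPG. Score unrepeated MBT failures as CSPH not ruled out, in line with 12.7.5, and separately as incorrect, labelled as a worst-case bound.
3. Report the number, reasons and rate of unrepeated MBT failures by CSPH status with exact 95% confidence intervals. Count patients who could not repeat within 7 days, so that exclusion 20 does not remove them from view, and separate failures of the test from other reasons for a missing result.
4. Reconcile the same-day MBT requirement for HCC patients (11.1, 13.1) with the bar on same-day repeats (Appendix III).

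The cost is one added table, built largely from termination forms and listings already planned, and possibly slightly less favourable figures.
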